### **6.3.3. Sensitivity Analysis for Key Secondary Efficacy Endpoints**

#### **6.3.3.1. Per-Protocol Analysis**

The analyses of the key secondary efficacy endpoints will be repeated using the PP Analysis Set specified in Section 3.1.3.

#### **6.3.3.2. Missing Data Imputation Analyses**

The following imputation methods will be explored:

- Change from Baseline in the HAQ-DI score at Week 24
  - 1) MI: All subjects with baseline measurement will be included. The MI procedure replaces each missing value with a set of plausible values that represent the uncertainty about the right value to impute. Multiple imputed datasets will be generated based on linear regression models on observed HAQ-DI scores. These multiple imputed data sets are then analyzed by using the analysis method specified in Section 6.3.2 for complete data. The result of each set of imputed data will be combined using Rubin's rule {Rubin 1987} and provided. Stratification factors and baseline values will be included in the imputation model as covariates, and all available data at baseline and postbaseline visits up to the time point of interest will be included in the longitudinal model.
  - 2) Tipping point analysis: All subjects with baseline measurement will be included. To assess the robustness of analysis results for HAQ-DI change from Baseline at Week 24 under MNAR assumption, a set of shift parameter that adjust the imputed values for observation will be examined {Yuan 2014}. The shift parameter that alters the conclusion of the hypothesis testing for HAQ-DI change from Baseline at Week 24 under the MAR assumption will be reported as the tipping point and provided. The tipping point analysis will be conducted by iteratively assigning plausible outcomes to missing values for subjects in different treatment groups independently until the analyses conclusion is reversed. The same analysis method as specified in Section 6.3.2 will be applied when analyzing adjusted data generated under each plausible shift parameter.

- Change from Baseline in mTSS at Week 24
  - 1) MI: Similar MI procedure used for analyzing the change from Baseline in the HAQ-DI score at Week 24 will be performed for change from Baseline in the mTSS at Week 24.
  - 2) Tipping point analysis: Similar tipping point analysis method used for analyzing the change from Baseline in the HAQ-DI score at Week 24 will be performed.
- Proportion of subjects who achieve DAS28(CRP) < 2.6 at Week 24
  - 1) The analysis using the same logistic regression model specified in Section 6.3.2 will be performed by using OC and LOCF methods as described in Section 6.1.
  - 2) MI: All subjects with baseline measurement will be included. The MI procedure replaces each missing composite DAS28(CRP) value with a set of plausible values that represent the uncertainty about the right value to impute. Baseline value and stratification factors will be included in the imputation model as covariates, and all available data at baseline and all post-baseline visits through the last available visits will be included in the longitudinal model. The multiple imputed datasets will be generated. These multiple imputed data sets are then used to identify subjects with  $\text{DAS28(CRP)} \leq 3.2$  at Week 12, and analyzed by using the analysis method specified in Section 6.3.2 for complete data. The results from each set of imputed data sets will then be combined using Rubin's rule {Rubin 1987}.
  - 3) Tipping point analysis: Similar tipping point method as described in Section 6.2.4.2 will be applied to DAS28(CRP) < 2.6 response rate at Week 24.
- Change from Baseline in SF-36 PCS at Week 24
  - 1) MI: Similar MI procedure used for analyzing the change from Baseline in the HAQ-DI score at Week 24 will be performed.
  - 2) Tipping point analysis: Similar tipping point analysis method used for analyzing the change from Baseline in the HAQ-DI score at Week 24 will be performed.
- Change from Baseline in FACIT-Fatigue at Week 24
  - 1) MI: Similar MI procedure used for analyzing the change from Baseline in the HAQ-DI score at Week 24 will be performed.
  - 2) Tipping point analysis: Similar tipping point analysis method used for analyzing the change from Baseline in the HAQ-DI score at Week 24 will be performed.

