### 3.5. Multiple Comparisons

The primary endpoint for the study is the proportion of subjects who achieve ACR20 response at Week 24. The primary analyses will consist of a superiority test of filgotinib 200 mg in combination with MTX compared to MTX alone based on the ACR20 response rate at Week 24.

The following hypothesis testing for secondary analyses will commence after the primary analysis reaches statistical significance, and will be tested according to the hierarchical testing principle at the 2-sided 0.05 level. If a null hypothesis is not rejected, formal sequential testing will be stopped and only nominal significance will be reported for the remaining hypotheses:

- 1) Superiority of filgotinib 100 mg in combination with MTX compared to MTX alone based on ACR20 response rate at Week 24.
- 2) Superiority of filgotinib 200 mg in combination with MTX compared to MTX alone based on the change from Baseline in HAQ-DI at Week 24.
- 3) Superiority of filgotinib 100 mg in combination with MTX compared to MTX alone based on the change from Baseline in HAQ-DI at Week 24.

- 4) Superiority of filgotinib 200 mg in combination with MTX compared to MTX alone based on the change from Baseline in mTSS at Week 24.
- 5) Superiority of filgotinib 100 mg in combination with MTX compared to MTX alone based on the change from Baseline in mTSS at Week 24.
- 6) Superiority of filgotinib 200 mg alone compared to MTX alone based on ACR20 response rate at Week 24.
- 7) Superiority of filgotinib 200 mg alone compared to MTX alone based on the change from Baseline in HAQ-DI to Week 24.
- 8) Superiority of filgotinib 200 mg in combination with MTX compared to MTX alone based on the proportion of subjects with DAS28(CRP) < 2.6 at Week 24.
- 9) Superiority of filgotinib 100 mg in combination with MTX compared to MTX alone based on the proportion of subjects with DAS28(CRP) < 2.6 at Week 24.
- 10) Superiority of filgotinib 200 mg alone compared to MTX alone based on the proportion of subjects with DAS28(CRP) < 2.6 at Week 24.
- 11) Superiority of filgotinib 200 mg alone compared to MTX alone based on the change from Baseline in mTSS at Week 24.
- 12) Superiority of filgotinib 200 mg in combination with MTX compared to MTX alone based on the change from Baseline in SF-36 physical component score (PCS) at Week 24.
- 13) Superiority of filgotinib 100 mg in combination with MTX compared to MTX alone based on the change from Baseline in SF-36 PCS at Week 24.

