### 3.8.2. Analysis Visit Windows

Subject visits may not occur on protocol-specified days. Therefore, for the purpose of analysis, observations will be assigned to analysis windows.

In general, the baseline value will be the last nonmissing value on or prior to the first dose date of study drug, except for the mTSS baseline value. The mTSS baseline value will be derived based on the measurements collected on or prior to the first dose date of study drug + 14 days given the potential delay in scheduling an x-ray assessment..

For efficacy endpoints, vital signs, electrocardiogram (ECG), weight, lipid, and safety laboratory data, the analysis visit windows will be applied to data collected during the ‘on-treatment’ period. The ‘on-treatment’ period is defined as the last dose date of any study drug plus 7 days.

The analysis windows for on-treatment efficacy endpoints including joint count assessment, HAQ-DI (including subject’s pain assessment), subject’s global assessment (SGA), physician’s global assessment (PGA), serum CRP, CCI [REDACTED] and vital signs, weight, and safety laboratory data (lipid data excluded) are provided in [Table 3-1](#).

**Table 3-1. Analysis Visit Windows for On-treatment Joint Count Assessment, HAQ-DI, SGA, PGA, CRP, CCI [REDACTED] and Vital Signs, Weight, and Safety Laboratory Data (Lipid Data Excluded)**

Analysis Visit	Nominal Study Day	Lower Limit	Upper Limit
Baseline	1	(none)	1
Week 2	15	2	22
Week 4	29	23	43
Week 8	57	44	71
Week 12	85	72	99
Week 16	113	100	127
Week 20	141	128	155
Week 24	169	156	190
Week 30	211	191	232
Week 36	253	233	281
Week 44	309	282	337
Week 52	365	338	≥ 365

The analysis windows for on-treatment ECG data are provided in [Table 3-2](#).

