#### **Selection of Efficacy Data in the Event of Multiple Records in an Analysis Visit Window**

If multiple valid and nonmissing efficacy measurements exist in an analysis window, then records will be chosen based on the following rules if a single value is needed:

- The record closest to the nominal day for that visit will be selected
- If there are 2 records that are equidistant from the nominal day, or more than 1 record (with time known) on the selected day, the latest record will be taken
- If chronological order cannot be determined (eg, more than 1 record on the same day with time missing), for any given subject, the worst outcome will be selected.

For the calculation of composite endpoints including DAS28(CRP), ACR20/50/70, ACR-N, SDAI, and CDAI, we use the following steps unless otherwise specified:

- Step 1: Assign individual components to analysis visit windows defined in Section 3.8.2
- Step 2: Within each analysis visit window, select the component-level data based on the rules for selecting efficacy data as above
- Step 3: Calculate the composite endpoint based on the selected component-level data in Step 2.

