## 6.3.2. Analysis Methods for Key Secondary Efficacy Endpoints

Hypothesis testing on the key secondary efficacy endpoints will commence after the testing on the primary efficacy endpoint reaches statistical significance, and will be performed according to the hierarchical testing principle at the 2-sided 0.05 level as described in Section 3.5. If a null hypothesis is not rejected, formal sequential testing will be stopped and only nominal significance will be reported for the remaining hypotheses.

For proportion of subjects who achieve  $\text{DAS28(CRP)} < 2.6$  at Week 24, the similar logistic regression analysis with the same model specification as the primary endpoint analysis described in Section 6.2.3 will be adopted for the comparisons between treatment groups. The NRI method will be used to impute missing values. Comparisons will be made between each filgotinib dose group and the MTX alone group. The p-value from the logistic regression model will be reported for statistical inference. The 2-sided 95% CI of the response rate of  $\text{DAS28(CRP)} < 2.6$  at Week 24 based on normal approximation will be provided for each treatment group. In addition, non-stratified response rate difference between treatment groups with its 95% CI based on the normal approximation will be provided.

The change from Baseline in HAQ-DI at Week 24 will be analyzed using the mixed-effects model for repeated measures (MMRM) that include all available data at postbaseline visits. Subjects that have a baseline value and at least one postbaseline value are included in the analysis. The MMRM model will be used to evaluate treatment effect on change score from Baseline, with baseline value, stratification factors, treatment, visit, and treatment by visit interaction included as fixed effects and subject being the random effect. An unstructured variance-covariance matrix will be used. The Kenward-Roger method will be used to estimate the degrees of freedom. Missing change scores due to missing study visits or early withdrawal will not be otherwise imputed using the MMRM approach. The least squares (LS) means along

with the two-sided 95% CIs and the p-value for the difference in mean change from Baseline in HAQ-DI at Week 24 between each filgotinib dose group and MTX alone group from MMRM will be provided.

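### The multiple-imputation sensitivity analysis for DAS28(CRP) < 2.6 at Week 24 is written to score DAS28(CRP) ≤ 3.2 at Week 12

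*SAP*

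**What the plan says.** SAP Section 6.3.3.2 groups its missing-data analyses by key secondary endpoint. One group is headed "Proportion of subjects who achieve DAS28(CRP) < 2.6 at Week 24" and has three items: (1) observed case (OC) and LOCF, (2) MI, and (3) tipping point.

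The MI item imputes the composite DAS28(CRP) score from baseline, the stratification factors and all post-baseline visits. It then defines the response. The sentence begins "These multiple imputed data sets are then used to identify subjects with", gives the criterion DAS28(CRP) ≤ 3.2, and continues "at Week 12, and analyzed by using the analysis method specified in Section 6.3.2 for complete data". Results are pooled by Rubin's rule.

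The tipping-point item directly below it "will be applied to DAS28(CRP) < 2.6 response rate at Week 24".

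Section 6.3.2, which the MI item cites for its method, covers the proportion with DAS28(CRP) < 2.6 "at Week 24, the similar logistic regression analysis with the same model specification as the primary endpoint analysis". In Section 3.5, hypotheses 8, 9 and 10 compare each filgotinib group with MTX alone "based on the proportion of subjects with DAS28(CRP) < 2.6 at Week 24".

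**The concern.** The responder definition in the MI item disagrees with the heading above it in both cut-off and visit. That sentence is the only place where the item says what is to be analysed, so a programmer following the SAP would build the wrong binary outcome. DAS28(CRP) ≤ 3.2 at Week 12 is a real endpoint of this study, listed in Section 6.4 among the other secondary endpoints. The program would therefore run and give plausible output, with nothing to flag the error.

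At stake is one robustness check on hypotheses 8 to 10. For this endpoint, the MI item is the only planned analysis that imputes the continuous score from each subject's earlier visits and then dichotomises it. OC leaves missing values missing. LOCF is single imputation. The per-protocol repeat uses non-responder imputation. In the Appendix 6 tipping-point code, the imputation step uses treatment, strata and the binary DAS28 variable, with no earlier DAS28 values.

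**Working it through.** The error is textual, so the main check sets the places side by side.

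| Place | Cut-off | Visit |
|---|---|---|
| SAP 6.3.3.2, heading of the group | < 2.6 | Week 24 |
| SAP 6.3.3.2, MI item | **≤ 3.2** | **Week 12** |
| SAP 6.3.3.2, tipping-point item | < 2.6 | Week 24 |
| SAP 6.3.2, method cited by the MI item | < 2.6 | Week 24 |
| SAP 6.3, key secondary list | < 2.6 | Week 24 |
| SAP 3.5, hypotheses 8, 9, 10 | < 2.6 | Week 24 |
| SAP 6.3.4, subgroup analysis | < 2.6 | Week 24 |
| Protocol 8.1.3 and 8.5.2 | < 2.6 | Week 24 |

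Only the MI item differs.

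**Could it be a legitimate analysis of another endpoint, put in the wrong place?** No. Section 6.3.3 covers key secondary endpoints only, and none of the five is at Week 12 or uses ≤ 3.2. For DAS28(CRP) ≤ 3.2, Section 6.4.2 plans OC and LOCF as the sensitivity approach, not MI. Section 6.3.2 has no ≤ 3.2 endpoint to which its method could apply.

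**How far apart are the two definitions?**

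- Cut-off: 3.2 − 2.6 = 0.6 DAS28 units. Scores from 2.6 to 3.2 inclusive change from non-response to response.
- Visit: Section 6.1 builds composite scores by visit window ("Step 1: Assign individual components to analysis visit windows defined in Section 3.8.2"). In Table 3-1 of Section 3.8.2, the Week 12 window is Days 72–99 (nominal Day 85) and the Week 24 window is Days 156–190 (nominal Day 169).
  - Nominal days: 169 − 85 = 84 days apart.
  - Days between the windows: 155 − 100 + 1 = 56, which are the Week 16 and Week 20 windows. No day is shared.
  - This applies to observed scores. An imputed score is drawn for the visit as a composite and has no component measurements.

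**How many analyses are affected?** The sensitivity analyses for this endpoint are OC, LOCF, MI and tipping point (Section 6.3.3.2) and per-protocol (Section 6.3.3.1), five in all. One is affected.

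**Effect on the response rates.** At a fixed visit, the looser cut-off can only raise the response rate. But the visit changes too, and the documents give no DAS28 response rates for this MTX-naïve population. The net change within an arm, and the change in the difference between arms, cannot be derived.

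**The case against.** The strongest reply is that this is a drafting slip that a careful reader would correct. The heading, the cited method, the neighbouring item and the hierarchy all give the intended endpoint. Section 6.3.3.2 presents its methods as exploratory, and no confirmatory test depends on them. The imputation step is not tied to Week 12, so imputed Week 24 scores would exist and only the responder flag is wrong. The tipping-point analysis is itself based on multiple imputation (Appendix 6 uses 20 imputations) and targets the right endpoint, so hypotheses 8 to 10 would not be left without any imputation-based check. The silence of Section 6.5 proves little, because that section lists departures from protocol-specified analyses and the protocol specifies no MI analysis of this endpoint.

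Most of this stands, and it limits the weight of the point. This is an inconsistency, not a deliberate choice, and the day counts describe the mismatch without measuring a consequence. The count of five also treats OC and LOCF as two analyses, although the SAP lists them in one item.

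What the reply does not do is make the text right. The wrong phrase is the operative rule, no other passage corrects it, and an analysis meant to be prespecified should not rely on the programmer overriding it. The tipping-point code uses a different imputation model, and the SAP does not say whether its shift grid includes zero in both arms, which would give an unshifted MI result.

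**Conclusion.** The point holds. As written, the MI sensitivity analysis for DAS28(CRP) < 2.6 at Week 24 evaluates a different outcome at a different visit, and so does not test the robustness of hypotheses 8, 9 and 10 to missing Week 24 data.

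It affects one of five sensitivity analyses for one key secondary endpoint. The non-responder logistic regression, the other four sensitivity analyses and the testing hierarchy are specified for the right endpoint. The conclusion needs no numerical assumption, and no size or direction is claimed for the effect on results. It should be fixed, but it does not threaten the confirmatory analysis.

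**What to change.** In the MI item of SAP Section 6.3.3.2, replace DAS28(CRP) ≤ 3.2 at Week 12 with DAS28(CRP) < 2.6 at Week 24, and check that the program derives the responder flag from the imputed Week 24 score with the < 2.6 cut-off.

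The cost is one phrase of SAP text and one program line. No new data are needed and the confirmatory analysis does not change. Made before the SAP is finalised, the correction keeps the analysis prespecified. Made later, it has to be documented in the clinical study report, as SAP Section 1 requires for changes after finalisation.

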#### **6.3.4. Subgroup Analysis of Key Secondary Endpoints**

Subgroup analysis comparing each filgotinib dose groups to the MTX alone group will be performed at Week 24 for the key secondary efficacy endpoint in the subgroups specified in Section 3.4.

The subgroup analysis for the proportion of subjects with DAS28(CRP) < 2.6 will be performed using the Fisher's exact test based on the NRI method. The number and percentage of subjects with DAS28(CRP) < 2.6 will also be provided for each treatment group within the subgroups

The change from Baseline in HAQ-DI will be analyzed using the MMRM method with baseline value, treatment, visit, and treatment by visit interaction included as fixed effects and subjects being the random effect. The LS mean, LS mean difference, SE, and 95% CI will be presented. The change from Baseline in mTSS, change from Baseline in SF-36 PCS and change from Baseline in FACIT-Fatigue will be analyzed similarly using the MMRM model, respectively. Descriptive statistics for actual values and change from baseline will also be presented for each treatment group within the subgroups.

#### **6.4. Other Secondary Efficacy Endpoints**

Other secondary efficacy endpoints include:

- Change from Baseline in the mTSS at Week 52
- The proportion of subjects who achieve ACR50 and ACR70 at Weeks 4, 12, 24, and 52, ACR20 at Weeks 4, 12, and 52, and ACR20/50/70 over time from Day 1 through Week 52
- Change from Baseline in individual components of the ACR response at Weeks 4, 12 and 24, and 52 and over time from Day 1 through Week 52
- The proportion of subjects who achieve change (ie, decrease) in HAQ-DI of  $\geq 0.22$  at Weeks 4, 12, 24, and 52, and over time from Day 1 through Week 52
- Change from Baseline in DAS28(CRP) at Weeks 4, 12, 24, and 52, and over time from Day 1 through Week 52
- The proportion of subjects who achieve DAS28(CRP)  $\leq 3.2$  at Weeks 4, 12, 24, and 52, and over time from Day 1 through Week 52
- The proportion of subjects who achieve DAS28(CRP) < 2.6 at Weeks 4, 12, and 52, and over time from Day 1 through Week 52
- ACR-N and European League Against Rheumatism (EULAR) response at Weeks 4, 12, 24 and 52, and over time from Day 1 through Week 52
- Change from Baseline in CDAI at Weeks 4, 12, 24, and 52, and over time from Day 1 through Week 52

- Change from Baseline in SDAI at Weeks 4, 12, 24, and 52, and over time from Day 1 through Week 52
- The proportion of subjects who had no radiographic progression from Baseline (applying threshold of 0.5 on change from baseline in mTSS) at Week 24 and 52
- Absolute value and change from Baseline in SF-36, FACIT-Fatigue, and the EQ-5D over time at Weeks 4, 12, 24, and 52, and over time from Day 1 through Week 52
- Absolute value and change from Baseline in WPAI-RA at Weeks 4, 12, 24, and 52, and over time from Day 1 through Week 52

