3. STUDY DESIGN

3.1. Endpoints

The primary endpoint is the proportion of subjects who achieve an ACR20 response at Week 24.

The key secondary endpoints are:

- Change from Baseline in the HAQ-DI score at Week 24
- The proportion of subjects who achieve DAS28 (CRP) <2.6 at Week 24
- Change from Baseline in mTSS at Week 24

Other secondary endpoints include:

- Change from Baseline in the mTSS at Week 52
- The proportion of subjects who achieve ACR50 and ACR70 at Weeks 4, 12, 24 and 52, ACR20 at Weeks 4, 12, and 52, and ACR20/50/70 over time from Day 1 through Week 52
- Change from Baseline in individual components of the ACR response at Weeks 4, 12, 24, and 52 and over time from Day 1 through Week 52
- The proportion of subjects who achieve improvement in HAQ-DI of ≥ 0.22 at Weeks 4, 12, 24, and 52, and over time from Day 1 through Week 52
- Change from Baseline in DAS28 (CRP) at Weeks 4, 12, 24, and 52, and over time from Day 1 through Week 52
- The proportion of subjects who achieve DAS28 (CRP) ≤ 3.2 at Weeks 4, 12, 24, and 52, and over time from Day 1 through Week 52
- The proportion of subjects who achieve DAS28 (CRP) <2.6 at Weeks 4, 12, and 52, and over time from Day 1 through Week 52
- ACR-N and EULAR response at Weeks 4, 12, 24, and 52, and over time from Day 1 through Week 52
- Change from Baseline in CDAI at Weeks 4, 12, 24, and 52, and over time from Day 1 through Week 52
- Change from Baseline in SDAI at Weeks 4, 12, 24, and 52, and over time from Day 1 through Week 24

- The proportion of subjects who had no radiographic progression from Baseline at Week 24 and 52
- Absolute value and change from Baseline in SF-36, FACIT-Fatigue, and the EQ-5D over time at Weeks 4, 12, 24 and 52, and over time from Day 1 through Week 52
- Absolute value and change from Baseline in WPAI-RA at Weeks 4, 12, 24, and 52, and over time from Day 1 through Week 52

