4.2. Inclusion Criteria

Subjects must meet all of the following inclusion criteria to be eligible for participation in this study.

- 1) Male or female subjects who are ≥ 18 years of age, on the day of signing informed consent.
- 2) Have a diagnosis of RA (2010 ACR/EULAR criteria) ([Appendix 8](#)), and are ACR functional class I-III
- 3) Have ≥ 6 swollen joints (from a SJC66) and ≥ 6 tender joints (from a TJC68) at both Screening and Day 1 (need not be the same joints) ([Appendix 7](#))
- 4) Must meet at least one of the following parameters at Screening:
 - ≥ 1 documented joint erosion on radiographs of the hands, wrists or feet by central reading
 - OR
 - positivity for either RF or anti-CCP Ab (based on central laboratory)
 - OR
 - Serum CRP ≥ 4 mg/L (based on central laboratory)
- 5) Have limited or no prior treatment with MTX, ie, no more than 3 doses of MTX ≤ 25 mg each in the subject's lifetime for the treatment of RA, with the last dose at least 28 days prior to Day 1, and are an appropriate candidate for MTX therapy, as per investigator judgment
- 6) Females of childbearing potential (as defined in [Appendix 5](#)) must have a negative pregnancy test at Screening and Day 1
- 7) Male subjects and female subjects of childbearing potential who engage in heterosexual intercourse must agree to use protocol specified method(s) of contraception as described in [Appendix 5](#)
- 8) Lactating female subjects must agree to discontinue nursing from Screening through the end of their study participation.

9) Meet one of the following tuberculosis (TB) Screening criteria:

a) No evidence of active or latent TB:

- A negative QuantiFERON[®] TB-Gold In-Tube test at Screening and
- A chest radiograph (views as per local guidelines) taken at Screening or within the 3 months prior to Screening (with the report or films available for investigator review) without evidence of active or latent TB infection and
- No history of either untreated or inadequately treated latent or active TB infection

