### 6.2.1. Definition of the Primary Efficacy Endpoint

A subject achieves ACR20 response when this subject has

- $\geq 20\%$  improvement from baseline in TJC68, AND
- $\geq 20\%$  improvement from baseline in SJC66, AND
- $\geq 20\%$  improvement from baseline in at least 3 of the following 5 items:
  - a) PGA
  - b) SGA
  - c) Subject's pain assessment
  - d) HAQ-DI score
  - e) hsCRP

Percent improvement from baseline at a postbaseline visit is calculated as follows for all 7 components mentioned above:

$$\% \text{ improvement} = \frac{\text{baseline value} - \text{postbaseline value}}{\text{baseline value}} \times 100$$

If the baseline value is 0, then the percent improvement from baseline is set to missing.

In the case that some ACR20 components are missing other than TJC68 or SJC66, the ACR20 assessment will be based on the non-missing components. If non-missing components are not sufficient to determine ACR20 response, then the ACR20 response will be considered as missing.

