##### 6.4.1.3. ACR-N

ACR-N is defined as the smallest percentage improvement from baseline in swollen joints, tender joints and the median of the following 5 items (PGA, SGA, subject's pain assessment, HAQ-DI and CRP). It has a range between 0 and 100%. In particular,

ACR-N = min { improvement in TJC68 (%), improvement in SJC66 (%), median [improvement in SGA (%), improvement in PGA (%), improvement in pain assessment (%), improvement in HAQ-DI (%), improvement in hsCRP (%)] }.

If this calculation results in a negative value, then the ACR-N is set to 0. If any components are missing, the ACR-N will be set as missing.

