## **Appendix 2. Health Assessment Questionnaire Disability Index (HAQ-DI)**

The HAQ-DI score is defined as the average of the scores of eight functional categories (dressing and grooming, arising, eating, walking, hygiene, reach, grip, and other activities), usually administered by the patient. Responses in each functional category are collected as 0 (without any difficulty) to 3 (unable to do a task in that area), with or without aids or devices.

The highest score for questions in each category (range 0 to 3) determines the score for the category, unless aids or devices are required. Dependence on equipment or physical assistance increases a lower score (ie, scores of 0 or 1) to the level of 2 to more accurately represent underlying disability. The eight category scores are averaged into an overall HAQ-DI score on a scale from 0 (no disability) to 3 (completely disabled) when 6 or more categories are non-missing. If more than 2 categories are missing, the HAQ-DI score is set to missing. The HAQ-DI can be treated as a continuous measure.

The HAQ-DI score using aids (and/or devices) is computed by taking the maximum score of the questions in each category (range: [0, 3]) and whether or not aids/devices are used (0 or 1):

$$A = \max(\text{dressing \& grooming category questions, } 2 * \text{aids indicator}) + \\ \max(\text{rising category questions, } 2 * \text{aids indicator}) + \\ \max(\text{eating category questions, } 2 * \text{aids indicator}) + \\ \max(\text{walking category questions, } 2 * \text{aids indicator}) + \\ \max(\text{hygiene category questions, } 2 * \text{aids indicator}) + \\ \max(\text{reach category questions, } 2 * \text{aids indicator}) + \\ \max(\text{grip category questions, } 2 * \text{aids indicator}) + \\ \max(\text{usual activities category questions, } 2 * \text{aids indicator})$$

$$\text{HAQ-DI} = A / (\text{total number of categories with at least 6 non-missing})$$

The following table shows the contribution of the 43 questions used to calculate the HAQ-DI:

HAQ-DI Category:	Category questions: At least 6 categories must have scores to compute the HAQ-DI.		HAQ-DI Category Score with Aids/Devices Calculation:
	Category Questions	Aids/Devices Indicators	

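### Subjects who enter with a HAQ-DI below 0.22 are fixed non-responders on the HAQ-DI responder endpoint, and those at 0 drop out of ACR-N; a baseline filter and one scoring sentence would repair both cheaply.

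*SAP*

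**What the plan says.** **Entry.** Protocol 4.2 requires joint counts plus erosion, serology or CRP. On function it says only that subjects "are ACR functional class I-III". Neither 4.2 nor 4.3 sets a minimum HAQ-DI.

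**The score.** SAP Appendix 2: "The eight category scores are averaged into an overall HAQ-DI score on a scale from 0 (no disability) to 3 (completely disabled"). One or two missing categories are tolerated: "If more than 2 categories are missing, the HAQ-DI score is set to missing".

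**The responder endpoint.** Protocol 3.1 lists "The proportion of subjects who achieve improvement in HAQ-DI of ≥ 0.22 at Weeks 4, 12, 24, and 52", and SAP 6.4 repeats it ("The proportion of subjects who achieve change (ie, decrease) in HAQ-DI of" at least 0.22). SAP 6.4.2 analyses it in the FAS by the same logistic regression with NRI as the primary endpoint. Under SAP 6.2.3 that model holds treatment and the stratification factors; baseline HAQ-DI is not in it, and no baseline restriction is stated.

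**ACR-N.** SAP 6.2.1, for all seven ACR components: "If the baseline value is 0, then the percent improvement from baseline is set to missing". SAP 6.4.1.3: "If any components are missing, the ACR-N will be set as missing". SAP 6.1 repeats the ACR-N rule under observed case. SAP 6.4.2 summarises ACR-N and also compares it between arms by MMRM.

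**Status.** Both are other secondary endpoints with nominal p-values (SAP 6.4.2), outside the testing hierarchy in SAP 3.5.

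**The concern.** A responder threshold has meaning only for a subject who has room to cross it. HAQ-DI has a floor of 0, so anyone who starts below 0.22 is a failure before the first dose. The plan keeps these subjects in the denominator of every arm, and nothing in the model accounts for them. The reported rate then mixes treatment effect with the baseline distribution of disability, and the between-arm difference is smaller than it is among subjects who could respond.

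The ACR-N rule has a different consequence. A subject with baseline HAQ-DI 0 is scored on the primary endpoint but silently absent from its continuous counterpart, at every visit. LOCF cannot recover the value, because the problem lies in the baseline.

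At stake are precision and the readability of two secondary results, not the confirmatory conclusions.

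**Working it through.** **1. The plan's own figures.** For mTSS, n = 2(1.960 + 1.282)² × (2.7/0.62)² = 399 per arm, and 400 per arm gives 90.1% power. The stated 400 and 90% reproduce. For ACR20 at 62% versus 78%, power is 99.9% with 400 per arm and 98.8% with 400 versus 200 (98.3% with a pooled null variance), so the stated figure of over 90% also holds. No figure is given for the HAQ-DI responder endpoint or ACR-N.

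**2. Who cannot respond.** Scores lie on a grid of 1/k, where k is the number of categories scored:
- k = 8: below 0.22 are 0 and 0.125 (the next score is 0.25)
- k = 7: 0 and 0.143 (next 0.286)
- k = 6: 0 and 0.167 (next 0.333)

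The largest possible fall equals the baseline score, so each of these subjects is a non-responder at every visit, whether observed or imputed.

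**3. Effect on the responder comparison.** Let f be the share below 0.22, equal across arms by randomisation, and let p be the response rate among those who can respond. The whole-FAS rate is p(1 − f), and the risk difference is multiplied by (1 − f). Restricting to baseline of at least 0.22 leaves the rate at p with n(1 − f) subjects per arm. Power = Φ(difference/SE − 1.96), with unpooled SE.

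The documents give neither f nor p, so both are assumptions. One pair of rates is 85% versus 75%. The other is 78% versus 62%, borrowed from the ACR20 planning rates. At f = 5% and 400 per arm:
- 85% versus 75%, whole FAS: 80.75% versus 71.25%; 0.0950/0.0300 gives z = 3.165 and power 88.6%. Restricted: 0.100/0.0288 gives z = 3.473 and power 93.5%. Ratio of squared z: 1.20.
- 78% versus 62%, whole FAS: 74.1% versus 58.9%; 0.152/0.0329 gives z = 4.615 and power 99.6%. Restricted: 0.160/0.0327 gives z = 4.888 and power 99.8%. Ratio of squared z: 1.12.

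Power over a range of f (whole FAS / restricted):

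| f | 85 v 75, 400 v 400 | 85 v 75, 200 v 400 | 78 v 62, 400 v 400 | 78 v 62, 200 v 400 |
|---|---|---|---|---|
| 2% | 92.4 / 94.2 | 81.3 / 84.5 | 99.8 / 99.9 | 98.2 / 98.6 |
| 5% | 88.6 / 93.5 | 75.4 / 83.4 | 99.6 / 99.8 | 97.0 / 98.4 |
| 10% | 81.3 / 92.2 | 65.8 / 81.4 | 98.9 / 99.7 | 94.2 / 97.9 |

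The 200 v 400 columns apply to the two filgotinib arms of 200.

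**4. Effect on ACR-N.** A baseline HAQ-DI of 0 makes that item's percent improvement missing at every visit, and hence ACR-N missing at every visit. ACR20 for the same subject can still be met on three of the other four items, together with both joint counts. Exclusion depends only on a pre-treatment value, so the difference among the remaining subjects is not shrunk. If a share f₀ is at 0, SE is multiplied by 1/√(1 − f₀): up 0.5% at 1%, 2.6% at 5% and 5.4% at 10%.

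**The case against.** **No material share may enter below 0.22.** Every subject needs at least 6 swollen and 6 tender joints at both Screening and Day 1, and the documents do not tie functional class I to any HAQ-DI value. This stands. The entry criteria permit such subjects. A reader might infer that they are enrolled by design, or that f reaches 10%; nothing in the documents shows either.

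**The power illustration depends on the rates chosen.** This also stands. A high response rate with a modest difference makes the loss look larger, and with the ACR20 planning rates it nearly vanishes at 400 per arm. Both are shown for that reason.

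**The whole-FAS proportion is a legitimate estimand, correctly estimated.** True. The restricted analysis describes a different, narrower population, which is why the whole-FAS rate should stay in the table.

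**Physical function is covered better elsewhere.** Change in HAQ-DI is a key secondary endpoint, analysed by MMRM with baseline as a covariate and backed by multiple imputation and tipping-point analyses. That limits the consequence of this point. It does not make the dichotomised rate easier to read.

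**The ACR-N rule is explicit and pre-specified.** It is, and a median over fewer items departs from the five-item definition. Reporting the number excluded per arm is the minimum alternative.

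**A stronger reading to avoid.** A reader might infer that both comparisons are diluted. Only the responder comparison is. In ACR-N the subjects are removed rather than counted as failures, so the cost is sample size and a narrower population.

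**Conclusion.** Both mechanisms follow from the SAP text. In the responder analysis, subjects below 0.22 at baseline are fixed failures and the risk difference shrinks by exactly (1 − f); for example, 16.0 points becomes 15.2 at an assumed f of 5%. Restricting to subjects who can respond is then worth about 12% to 20% more sample under the two sets of assumed rates. In ACR-N, subjects at HAQ-DI 0 are lost, with SE up about 2.6% if 5% are at 0, and the result no longer describes the full set on which ACR20 is scored.

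The size rests wholly on assumed shares and response rates. No between-arm bias arises, no type I error is affected, and no test in the hierarchy depends on either endpoint. This is a cheap improvement, not a defect in the confirmatory plan.

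**What to change.** **SAP 6.4.2.** Analyse a HAQ-DI decrease of at least 0.22 in FAS subjects with baseline HAQ-DI of at least 0.22, with NRI unchanged. Keep the whole-FAS rate as a supportive row and report the number excluded per arm. The filter also covers the 0.143 and 0.167 cases. State where subjects with no baseline HAQ-DI are placed.

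**SAP 6.4.1.3.** When an item's baseline is 0, take the ACR-N median over the remaining items, in line with the ACR20 practice of using the non-missing components. Report the number affected per arm.

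**Cost.** A few sentences of SAP wording and a baseline filter. The responder denominator becomes slightly smaller and differs from the other response endpoints, and ACR-N departs slightly from its five-item median. The subset is defined before treatment, so the randomised comparison is preserved. The SAP already limits three WPAI-RA scores to subjects employed at baseline and postbaseline, so a restriction to those in whom an outcome can be assessed is not new to the plan. The change should be written before unblinding, since a later restriction would look data-driven.
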